9.2 Performance Goals

The performance goals used for the hypotheses in section 4.3 and the sample size calculations in section 9.1 were derived from the pivotal study of the Zenith AAA Endovascular Graft. The 30-day freedom from MAEs was 98.3% and the 12-month device success was 93.0% in the pivotal study of the Zenith AAA Endovascular Graft. Therefore, the performance goals of 88% for freedom from MAEs and 83% for device success, respectively, have been determined.

9.3 Site-level Poolability

Poolability of data from multiple sites will be verified by examining the safety and efficacy measures as well as important patient baseline characteristics among sites. Site-level poolability will be considered appropriate provided that these measures are similar among sites.

9.4 Missing Data

Missing data will be addressed using three primary strategies: 1) estimating missing data with the best available data, 2) case deletion, and 3) multiple imputation.

The first strategy may be used for missing imaging data. Previous clinical trial experience suggests that some portion of the imaging data may not meet the criteria for accurate measurements by the core laboratory. However, it is recognized that the treating physician uses this information to provide the best possible care for the patient. Therefore, it is reasonable to substitute any missing core laboratory measurements with the corresponding measurements made by the treating physician (or his/her staff). In addition, the absence or presence of clinical sequelae may provide the required missing core laboratory assessment of device performance. This strategy is a best approximation of the missing data value.

The second strategy is case deletion. If the amount of missing data does not result in a reduction of analyzable patients to a number that is below that required for sufficient statistical power of the endpoints, then case deletion will be the method of choice for that analysis.

The third method is multiple imputation. This method will be used to predict missing endpoint or covariate data. It may be that the study endpoints may depend upon certain covariates. Therefore, it may be possible to model study endpoints, given a series of related covariates. This model-based imputation exercise may provide estimates of the missing data that can be utilized in estimating event rates and confidence bounds.

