4.2 Claims and Intended Performance that are to be Verified

The following data points will be evaluated to verify device performance:

- Device success (including technical success)
- Procedural times
- Access method (percutaneous, cutdown, or conduit usage) employed during the procedure
- Clinical utility measures
- Morbidity, including Major Adverse Events (MAEs) as well as events distal to the graft limb (e.g., arterial thrombosis)
- Reinterventions-
- Endoleak, change in aneurysm size, migration, device patency, device integrity

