4.3 Specific Hypotheses to be Accepted or Rejected by Statistical Data

The safety endpoint of 30-day freedom from MAEs will be analyzed on a per patient basis. The analysis requires that the agreed upon performance goal of 88%, which was derived from the 30-day freedom from MAE rate for patients treated with the currently approved Zenith AAA Endovascular Graft, be met. The performance goal will be said to have been met provided that the null hypothesis is rejected in favor of the alternate with a one-tailed exact binomial test at the 0.025-level. Given that $\pi_{MAE(30)}$ is the probability that a randomly selected patient experienced freedom from MAEs at 30 days, the null and alternate hypotheses are as follows.

Null Hypothesis: The 30-day freedom from MAEs for patients treated with the Zenith Low Profile AAA Endovascular Graft in conjunction with the Zenith Spiral-Z AAA Iliac Leg Graft does not meet the performance goal (88%).

$$H_0: \pi_{MAE(30)} < 88\%$$

Alternate Hypothesis: The 30-day freedom from MAEs for patients treated with the Zenith Low Profile AAA Endovascular Graft in conjunction with the Zenith Spiral-Z AAA Iliac Leg Graft meets the performance goal (88%).

$$H_A: \pi_{MAE(30)} \geq 88\%$$

Similarly, the effectiveness endpoint of 12-month device success will be analyzed on a per patient basis. The analysis requires that the agreed upon performance goal of 83%, which was derived from the 12-month device success rate for patients treated with the currently approved Zenith AAA Endovascular Graft, be met. The performance goal will be said to have been met provided that the null hypothesis is rejected in favor of the alternate with a one-tailed exact binomial test at the 0.025-level. Given that $\pi_{DS(12)}$ is the probability that a randomly selected patient experienced device success at 12 months, the null and alternate hypotheses are as follows.

Null Hypothesis: The 12-month device success for patients treated with the Zenith Low Profile AAA Endovascular Graft in conjunction with the Zenith Spiral-Z AAA Iliac Leg Graft does not meet the performance goal (83%).

$$H_0: \pi_{DS(12)} < 83\%$$

Alternate Hypothesis: The 12-month device success for patients treated with the Zenith Low Profile AAA Endovascular Graft in conjunction with the Zenith Spiral-Z AAA Iliac Leg Graft meets the performance goal (83%).

$$H_A: \pi_{DS(12)} \geq 83\%$$

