9.0 Statistical Considerations

9.1 Sample Size Calculations

Evaluation of the safety hypothesis, 30-day freedom from MAEs, requires 46 patients to determine whether the performance goal of 88% has been met. Evaluation of the effectiveness hypothesis, 12-month device success, requires 59 patients to determine whether the performance goal of 83% has been met. Cook intends to enroll 120 patients to account for patients who withdraw or are lost to follow-up, and also to provide added enhanced statistical certainty as well as the same number of patients as agreed to for a previous similar study.

Sample size calculations for the safety and effectiveness hypotheses can be performed with the following assumptions. Using performance goals of 88% for freedom from MAEs and 83% for device success, with an expected rate of 99.2% for freedom from MAEs and 93.5% for device success, an exact binomial calculation, $\alpha=0.025$, power=0.80 and a one-sided test, 46 patients for freedom

from MAEs and 59 patients for device success are required to demonstrate that the Zenith Low Profile AAA Endovascular Graft in conjunction with the Zenith Spiral-Z AAA Iliac Leg Graft meets the stated performance goals.

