MI (Non-Q-Wave): Investigator identified patients having clinical evidence of a myocardial infarction with elevated peak CK values greater than or equal to three times the upper limit of normal with elevated CK-MB (above the institution's upper limit of normal) in the absence of new pathological Q-waves or clinical evidence of a myocardial infarction with troponin greater than three times the upper limit of normal, as determined by the investigator.

MI (Q-Wave): Post-procedure presence of new Q-waves greater than 0.04 seconds in at least two EKG leads.

Renal Failure: Acute or progressive renal insufficiency leading to the need for dialysis or hemofiltration.

Renal Insufficiency: A rise in serum creatinine of more than 30% above the pre-procedure level, resulting in a serum creatinine level >2.0 mg/dl that does not spontaneously resolve (does not include those patients with a pre-procedure serum creatinine >2.0 mg/dl).

Embolization: Clinical evidence of ischemic tissue remote from the operative field, presumably caused by thrombus dislodged from the aneurysmal sac, aortic neck, or adjacent vessels, including ischemia of the kidneys, pelvis (IIA) or lower limbs. This is, of course, distinct from intentional pre-operative, operative, or post-operative embolization procedures.

Graft Limb Occlusion: The presence of thrombus within one, or both, of the graft limbs (including any legs and extensions) creating complete occlusion with no blood flow through the graft limb.

Graft Lumen Diameter: The diameter measured inner wall to inner wall within the endograft.

Type I Endoleak: A peri-prosthetic leak occurring at the proximal and/or distal fixation zones.

Type II Endoleak: A leak caused by retrograde flow from patent lumbar or inferior mesenteric arteries or other collateral vessels.

Type III Endoleak: A leak caused by a defect in the graft fabric, or inadequate seal of modular graft components.

Type IV Endoleak: A leak caused by graft fabric porosity, often resulting in a generalized blush of contrast within the aneurysm sac.

Endoleak (early): Any endoleak observed within 30 days of device deployment.

Endoleak (late): Any endoleak observed later than 30 days after device deployment that was not documented during the first 30 days post-deployment.

Radiographic Migration

(stent-graft): Antegrade or retrograde movement of the stent-graft ≥ 10 mm at the level of the renal arteries as compared to the position on the first post-operative CT scan.

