Clinical Utility

Measures: Duration of procedural intubation; days to resumption of oral fluids; days to resumption of normal diet; days to resumption of normal bowel function; days to ambulation; duration of ICU stay; days to discharge.

Clinically Significant Migration

(stent-graft): Antegrade or retrograde movement of the stent-graft requiring surgical or endovascular intervention.

Barb Separation: Radiographic evidence of detachment of barbs from the stent strut as confirmed by the CEC.

Stent/attachment System

Fracture/break: Fracture or breakage of any portion of the stent or attachment system including metallic fracture or breakage of any suture material used to construct the stent or secure the stent or attachment system to the graft material as confirmed by the CEC.

Technical Success: Successful access of the aneurysm site and deployment of the Zenith Low Profile AAA Endovascular Graft and the Zenith Spiral-Z AAA Iliac Leg Graft in the intended location. The endovascular graft must be patent at the

time of deployment completion as evidenced by intraoperative angiography.

Device Success

(12-month):

Technical Success, with none of the following at 12 months:

- Type I or type III endoleaks requiring re-intervention;
- Graft limb occlusion;
- Aneurysm rupture or conversion to open surgical repair; or
- Aneurysm enlargement greater than 0.5 cm.

Major Adverse Events: All-cause death, Q-wave MI, renal failure requiring dialysis, paralysis, stroke, bowel ischemia, re-intubation.

Serious Adverse

Event:

An adverse event that led to death, led to a serious deterioration in the health of the subject that resulted in a life-threatening illness or injury, resulted in a permanent impairment of a body structure or a body function, required in-patient hospitalization or prolongation of existing hospitalization, resulted in medical or surgical intervention to prevent permanent impairment to body structure or a body function, led to fetal distress, fetal death, a congenital abnormality or birth defect.

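### Section 9.4 does not limit by component when absent clinical sequelae may stand in for a missing core-lab assessment, so an unread enlargement or limb occlusion could be scored as no failure

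*Combined protocol and SAP*

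**What the plan says.** Section 9.4 names three ways to deal with missing data: best available data, case deletion and multiple imputation. On the first it says: "The first strategy may be used for missing imaging data". It describes two substitutes. A missing core-lab measurement may be replaced by the treating physician's measurement. In addition, "the absence or presence of clinical sequelae may provide the required missing core laboratory assessment of device performance". No component of the endpoint is named, sequelae are not defined, and no order is set between the two substitutes. On the second strategy, if enough analysable patients remain for sufficient power, "case deletion will be the method of choice for that analysis".

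Attachment 2 defines 12-month device success as technical success with none of the following: type I or III endoleak requiring re-intervention, graft limb occlusion, rupture or conversion to open repair, and "Aneurysm enlargement greater than 0.5 cm". It defines limb occlusion as thrombus "creating complete occlusion with no blood flow through the graft limb". Section 4.2 lists, among the data points used to verify device performance, "Endoleak, change in aneurysm size, migration, device patency, device integrity". Section 4.3 tests device success against 83% with "a one-tailed exact binomial test at the 0.025-level".

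**The concern.** Rupture, conversion and re-intervention for endoleak leave a clinical record, so clinical information can settle them. Enlargement and limb occlusion are different. One is a size threshold and the other a statement about flow, and neither definition refers to symptoms. The documents do not say how often an occlusion is symptom-free; that it can be is inferred from the definition. Enlargement is the clearer case, because an occlusion may well cause symptoms.

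If the image is unread and the patient is well, the absence of sequelae does not show that either failure is absent. Inferring no failure can turn a failure into a success but never the reverse, so the error has one direction. In a single-arm, unblinded study against a fixed goal, nothing offsets it. The wording also leaves two routes open for the same patient, scored as a success or deleted, and does not require the choice to be made before the data are seen.

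**Working it through.** **Inputs from the documents.** Goal p0 = 0.83, expected rate 0.935, one-sided α = 0.025, planned power 0.80 and required n = 59 (Sections 4.3 and 9.1); planned enrolment N = 120 (Section 9.1).

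**Inputs assumed.** m is the share of patients with neither a core-lab nor a site reading. s is the share of failures that is silent, that is, visible only on an image. The documents give neither, so ranges are shown.

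**The plan's own figure.** Section 9.1 states: "Evaluation of the effectiveness hypothesis, 12-month device success, requires 59 patients". This does not reproduce at α = 0.025. With n = 59 the exact test needs at least 55 successes (α = 0.0196), and power at 0.935 is 66.2%. The smallest n with 80% power is 81 (at least 74 successes, α = 0.0250, power 84.4%). The figure 59 appears at α = 0.05 (at least 54 of 59, power 81.6%). That is a separate matter. It bears on this point only because the deletion rule in Section 9.4 refers to the number needed for sufficient power.

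**Baseline at N = 120.** P(X ≥ 107 | 0.83) = 0.0412 and P(X ≥ 108 | 0.83) = 0.0222, so the goal is met at 108 or more. Power is P(X ≥ 108 | 0.935) = 95.1%.

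**Effect of using the clause.** If silent failures among unread patients are scored as successes, the apparent success rate is 0.83 + m × 0.17 × s. For m = 5% and s = 0.5 it is 0.83 + 0.05 × 0.17 × 0.5 = 0.83425. Type I error is P(X ≥ 108) at that rate:

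| m | s = 0.25 | s = 0.5 | s = 1 |
|---|---|---|---|
| 1% | 0.0228 | 0.0235 | 0.0248 |
| 2% | 0.0235 | 0.0248 | 0.0277 |
| 5% | 0.0255 | 0.0292 | 0.0381 |
| 10% | 0.0292 | 0.0381 | 0.0630 |

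The error reaches 0.025 at m × s = 0.0108, so it passes the nominal level only when that product is above about 1.1%. The s = 1 column is an upper bound, because technical failure, rupture, conversion and re-intervention are visible without a 12-month image.

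The expected number wrongly scored as success is 120 × m × 0.17 × s: 0.2 patients at m = 2%, s = 0.5; 0.5 at m = 5%, s = 0.5; 2.0 at m = 10%, s = 1. At the planned 93.5% the factor 0.17 becomes 0.065, giving 0.2 at m = 5%, s = 0.5.

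**Effect of the fix, if the unread are deleted.** Clinically well unread patients are deleted with probability d = m × (p + (1 − p) × s), and unread clinical failures are kept. Then n ~ Bin(120, 1 − d), the success rate among those kept is (1 − m)p / (1 − d), and the critical value is recomputed for each n. Ranges are for s = 0.25 to 1:

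| m | Power at 93.5% | Type I error at 83% | Success rate among those kept, true 0.830 |
|---|---|---|---|
| 5% | 91.0–92.6% | 0.0122–0.0180 | 0.8245–0.8300 |
| 10% | 86.8–90.9% | 0.0081–0.0177 | 0.8184–0.8300 |

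Deletion of this kind is conservative: the rate among those kept is at or below the truth, because clinical failures stay and only clinically well patients leave.

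**The case against.** The strongest reply is that Section 9.4 already separates two things. Missing measurements go to the treating physician's measurements, and only an assessment is left to sequelae. Enlargement above 0.5 cm rests on a measurement, so on this reading it is largely shielded. This is a fair reading, and Section 4.2 does not defeat it. That list is not a definition of device performance as assessed by the core lab; it also contains procedural times and access method. But Section 9.4 does not state the division or set an order, and it does not say what happens when no site measurement exists. Patency is an assessment, so limb occlusion stays open to the clause on either reading.

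The second reply is that few patients are affected. They must have no core-lab and no site reading, yet a known clinical status. Site readings will usually exist, the 12-month clinical examination and CTA fall at the same visit, and Section 8.4 allows non-contrast CT with duplex ultrasound where contrast cannot be used. This stands, and it limits the size.

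A reader might also infer that deletion stays the preferred method until more than 120 − 59 = 61 patients are missing, so that imputation would hardly ever be reached. The documents do not support this. Section 9.4 refers to sufficient power and does not name 59, and 59 gives only 66.2% at the stated α. Taking 81 instead, the threshold would be 120 − 81 = 39.

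**Conclusion.** The point holds as a gap in wording with a known direction and an unknown, probably small, size. Section 9.4 permits absent sequelae to clear a limb-occlusion component that nobody has read and, unless the measurement reading is intended, an enlargement component as well. With 2–5% unread and 25–100% of failures silent, type I error is 0.0235–0.0381 against 0.0222 with complete readings. These figures rest on assumed m and s and on true success exactly at 83%.

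Two stronger conclusions are tempting and not supported. First, the plan does not require this scoring, because the clause is permissive. Second, the figures do not show that the test is invalid: type I error stays below 0.025 at every s with 1% unread, and 0.0630 needs 10% unread with every failure silent. Nor do the documents show anything wrong with using site readings. The point is a minor one that should still be corrected, because the correction is cheap and the choice should not stay open once outcomes are known.

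**What to change.** In Section 9.4:

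- State that absence of clinical sequelae may not clear the enlargement or limb-occlusion component without a core-lab or site image reading. Clinical records remain valid for rupture, conversion and endoleak requiring re-intervention, and presence of sequelae may still count as failure.
- Where neither reading exists and no clinical failure is recorded, treat the component as missing. Handle it by one method from Section 9.4, fixed before the data are seen. If deletion is chosen, note that removing only clinically well patients is conservative. If multiple imputation is chosen, say how the result is tested, since the exact binomial test in Section 4.3 needs a whole count.
- Add a tipping-point sensitivity analysis over the unread patients. Counting all of them as failures belongs at the end of that range and not in the primary analysis: P(X ≥ 108) at 0.935 × (1 − m) is 80% at m = 2% and 41% at m = 5%.

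The cost is a few sentences and one extra analysis, with no new imaging or readers. A few patients move to missing. Under deletion, power falls from 95.1% to 91.0–92.6% with 5% unread and 86.8–90.9% with 10% unread, still above the planned 80%.

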9.5 Future Use of Study Data

The data collected in this study may be used to justify additional studies of variations on the Zenith Low Profile AAA Endovascular Graft including, but not limited to, design variations. It is anticipated that the safety and effectiveness

data obtained may serve as prior information in the analysis of the safety and effectiveness of future variations of the Zenith Low Profile AAA Endovascular Graft.

10.0 Emergency Situations

Patients will not be treated with the Zenith Low Profile AAA Endovascular Graft in conjunction with the Zenith Spiral-Z AAA Iliac Leg Graft in emergency situations where prior consent of the patient is not possible.

11.0 Deviations from Clinical Investigation Plan

Investigators are not allowed to deviate from this Clinical Investigation Plan without prior authorization by the sponsor except under emergency situations when necessary to preserve the rights, safety, or well-being of study patients.

Deviations or noncompliances will be recorded together with an explanation. Deviations or noncompliances that impact the rights, welfare, or safety of patients shall be reported to the sponsor and Ethics Committee/IRB as required and as soon as possible. If appropriate, corrective and preventive actions will be discussed by the sponsor, investigator, and/or the Ethics Committee/IRB to determine a suitable course of action.

When available, the reasons for withdrawal and discontinuation of any patient from the investigation shall be recorded. If such discontinuation is because of problems with safety or lack of effectiveness of the device, that patient shall still be followed-up in the investigation, if possible.

12.0 Procedure for Reporting Adverse Events and Adverse Device Effects

Events known to be related to pre-existing conditions or existing at admission are not considered adverse events (e.g., prior medically-treated cardiac arrhythmia with no change in status during the endovascular procedure). Additionally, common standard of care practices are not considered adverse events (e.g., centers located at high geographical altitudes that discharge all patients on home oxygen therapy regardless of procedure).

All adverse events (i.e., device-related and non-device-related) are to be reported using the appropriate case report form (Adverse Event/Complication

form). In cases of adverse device effects (adverse event with relation to the study device) or serious adverse events, completed forms should be submitted to the Data Coordinating Center as soon as possible upon knowledge of the event.

MED Institute, Inc.
[name]
[name]
Telephone: [REDACTED]
Fax: [REDACTED]

The Data Coordinating Center will notify the sponsor/manufacturer accordingly. In accordance with applicable requirements, the investigator will notify the local Ethics Committee/IRB, while the sponsor/manufacturer will notify the regulatory authority. Furthermore, if the sponsor determines that the device presents a potential risk to the study patients, all investigators in the study will be notified. Clinical sites will be responsible for following their normal reporting process (e.g., to manufacturer, to regulatory authority) for any problems with the commercially available devices. Refer to section 7.1 for a list of potential adverse events related to this study.

13.0 Ethical Considerations

13.1 Declaration of Helsinki

The investigation shall be performed according to the ethical principles that have their origin in the Declaration of Helsinki and in accordance with ISO 14155, ICH GCP, and 21 CFR 812.

